1. INTRODUCTION

1.1 SUMMARY

Pain is a common co-morbidity for HIV-positive patients. Prevalence studies suggest that, on average, half of all HIV-positive persons suffer pain. Chronic pain can lead to heavy alcohol use among HIV-positive persons, which may in turn be a barrier to treatment/control of HIV and contribute to spread of HIV. Thus there is an urgent need to address pain among persons with HIV. We aim to perform a pilot RCT comparing low-dose naltrexone and gabapentin to placebo for improving pain, inflammation, and measures of HIV status among HIV-positive persons with chronic pain and heavy alcohol use. It is timely and relevant to conduct research on gabapentin. In this new era of judicious opioid prescribing it has emerged as one of the most commonly prescribed non-narcotic medications for pain. According to a recent review, gabapentin prescriptions increased from 44 to 68 million between 2013 and 2017, becoming the 10th most commonly prescribed medication in the United States.¹ This is despite the fact that gabapentin is only FDA approved for "post-herpetic neuralgia" and the literature to support its use in other pain conditions, and generalized chronic pain, are limited. And yet, gabapentin has demonstrated benefits for treatment of alcohol use disorder,² and therefore, like naltrexone, it could have a specific role for treating patients with chronic pain and unhealthy alcohol use.³

The specific aim of the research is to perform a 3-arm pilot randomized, double-blinded, placebo-controlled study of low-dose naltrexone and gabapentin vs. placebo among HIV-positive persons with heavy alcohol use and chronic pain to provide estimates of their effects on: 1) pain (both self-reported and experimental/cold pressor test; 2) inflammation (i.e., levels of inflammatory cytokines IL-6 and TNF- α); and 3) measures of HIV control (CD4 cell count and HIV viral load). We choose to conduct this research in St. Petersburg, Russia, given that: 1) patients are seldom on chronic opioids (which are contraindicated to use with opioid receptor antagonists) due to the unavailability of opioid agonist therapy for addiction and restricted use of opioids for pain; and 2) a high prevalence of heavy drinking and HIV exists in Russia.

During the UH2 component we found that K-opioid antagonist, nalmefene was not tolerable, leading us to modify the original research plan by replacing the nalmefene arm of the study with GABA analog, gabapentin. Given the US epidemic of opioid use disorders, new pharmacotherapies without addictive potential are desperately needed for HIV-positive persons with chronic pain and alcohol problems.

2. OVERVIEW OF STUDY DESIGN

2.1 STUDY AIMS

Our Specific Aim will compare effects of low-dose naltrexone and gabapentin to placebo among HIV-positive persons with heavy alcohol use and chronic pain:

UH3 Aim: To perform a 3-arm pilot, randomized, double-blinded, placebo-controlled study of low-dose naltrexone and gabapentin vs. placebo among HIV-positive persons with heavy alcohol use and chronic pain to provide estimates of their effects on 1) pain (both self-reported and experimental/cold pressor test); 2) inflammation (i.e., levels of inflammatory cytokines IL-6, IL-1 β , IL-10, and TNF- α); and 3) measures of HIV control (CD4 cell count and HIV viral load).

2.2 STUDY OUTCOMES

Primary Outcomes: The primary outcome for this study is change in past week pain severity and pain interference (score 0-10) from baseline to week 8. Pain severity and interference will be measured using the Brief Pain Inventory (BPI).

Secondary Outcomes:

Changes in the following secondary outcomes between baseline and week 8 will also be compared among the 3 arms:

- 1) Biomarkers IL-6, IL- β , 1L-10, and TNF- α . Levels of these pro-inflammatory markers will be measured on blood samples collected using commercially available enzyme-linked immunosorbent assay kits (R&D Systems).
- 2) Cold pain tolerance. This will be measured using the cold-pressor test; briefly it is the number of seconds a participant can keep hand submerged in cold water bath.

[figure not shown]
- 3) Percentage of past month heavy drinking days. We will use the Timeline Follow Back to assess drinks per day in the past 30 days. Using a calendar, people provide retrospective estimates of their daily drinking over the past 30 days from the interview date. Definitions of heavy drinking are based on NIAAA guidelines for at-risk drinking (i.e., drinking greater than 14 standard drinks per week/greater than 4 drinks in a day for men; greater than 7 drinks in the past week/greater than 3 drinks in a day for women).
- 4) Measures of HIV control: CD4 cell count and HIV viral load will be measured on participants.

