The purpose of the pilot trial is to generate preliminary data for design of a future larger RCT to demonstrate efficacy. Thus estimation rather than testing is the main objective of this aim. However we provide illustrative power calculations for our primary outcome (change in pain severity) based on prior literature and the number of participants (15 in each arm) we intend to study. It is expected that 45 participants will be enrolled into the study and less than 15% will drop out by 8 weeks. We therefore assume 39 participants (13 per arm) will complete the 8-week follow-up. The following calculations assume 2-sided tests, with an overall significance level of 0.05. For the purposes of power calculations, we consider a simple, conservative setting based on a Bonferroni adjustment for multiple comparisons, although in our analyses we will use the Hochberg sequential correction method, an approach that will result in higher power than the Bonferroni method. To maintain an overall type I error rate of 5%, we assume each of the 2 primary pairwise comparisons (i.e. each intervention vs. placebo) will be conducted at an alpha level of 0.025 for the following power calculations. Based on the 2013 study by Younger, the standard deviation for change in pain severity was 2.9. We expect the standard deviation will be similar in the proposed study and the same for each randomized group. Given this assumption, the minimum detectable difference in change in pain severity between baseline and 8 weeks that the study can detect with 80% power is 3.8 for either of the 2 primary comparisons of interest (i.e., naltrexone vs. placebo; gabapentin vs. placebo), (e.g., -3.0 vs. 0.8 for naltrexone vs. placebo, respectively) using a 2-sided t-test. Because a main goal of the study is estimation of effect sizes for the design of a future study, we also estimate the width of the confidence interval for the mean difference between any two arms for the primary outcome. Our calculations assume 2-sided 95% confidence intervals. Assuming a standard deviation of 2.9 as above, the 95% confidence interval for the mean difference in change in pain severity for either intervention arm vs. placebo would be no wider than 4.7.

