8. STATISTICAL ANALYSIS

This study will use an intent-to-treat analysis that includes all participants according to their randomized assignment. Descriptive statistics will be calculated for variables at baseline and each follow-up time to assess whether there appear to be any differences across treatment arms.

The main focus of this aim is the assessment the impact of each intervention (naltrexone, gabapentin, or placebo) on the primary study outcome (i.e., the continuous variable change in pain severity from baseline to week 8).

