8.1 PRIMARY ANALYSES

Descriptive statistics and graphic displays of all outcome measures will be generated.

The main analysis evaluating the impact of each intervention on the primary study outcome (i.e., the continuous variable change in pain severity and pain interference from baseline to week 8) will use multiple regression models to estimate mean differences between arms along with 95% confidence intervals. The models will include indicator variables to represent study arm. The 2 primary comparisons of interest are between each intervention vs. placebo, i.e., naltrexone vs. placebo; gabapentin vs. placebo, and will adjust for the multiple comparisons using the Hochberg sequential test procedure. We will compare naltrexone vs. gabapentin but these tests will be of secondary interest. If the data are normally distributed, multiple linear regression models will be used. However, if the distribution of change in pain severity is skewed, transformations of the data will be performed (e.g., log transformation). If an appropriate transformation is not identified, a median regression model will be used. Secondary outcomes (e.g., changes in biomarkers, cold pain tolerance) are continuous variables and will be analyzed using the same approach as above.

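### The primary outcome is BPI severity and interference in 2.2 and 8.1 but severity alone in 2.7.A and 8, and the Hochberg step is set for two tests, not four

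*Combined protocol and SAP*

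**What the plan says.** The combined protocol and SAP defines the primary outcome in four places, and they do not agree.

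- **Two scales.** Section 2.2 (Study Outcomes): "The primary outcome for this study is change in past week pain severity and pain interference (score 0-10) from baseline to week 8". Section 8.1 (Primary Analyses) describes the outcome of the main model as "the continuous variable change in pain severity and pain interference from baseline to week 8".
- **One scale.** Section 8 (Statistical Analysis), directly above 8.1, has "the continuous variable change in pain severity from baseline to week 8". Section 2.7.A (Sample Size Calculation and Power) offers "illustrative power calculations for our primary outcome (change in pain severity", and its only variability input is also for severity: "the standard deviation for change in pain severity was 2.9".

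Section 3.1 (Intervention Overview) mentions the scales twice. Its list of outcomes pairs severity and interference ahead of the biomarkers. Its week 8 list puts interference apart from the BPI pain item, between cold pain tolerance and heavy drinking days. The secondary list in 2.2 does not contain interference.

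On multiplicity, 2.7.A says: "To maintain an overall type I error rate of 5%, we assume each of the 2 primary pairwise comparisons", each at 0.025. Section 8.1 says: "The 2 primary comparisons of interest are between each intervention vs. placebo", and that the analysis "will adjust for the multiple comparisons using the Hochberg sequential test procedure". The detectable difference (3.8), the confidence interval width (4.7) and the rule for skewed data are also given for severity only.

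**The concern.** Two scales and two drug-placebo comparisons make four primary tests; one scale makes two. The plan adjusts for two. It does not rank the scales, define a combined score, or say whether a drug must succeed on one scale or on both.

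Suppose the severity result is null and the interference result is positive. Under 2.2 and 8.1 that can be reported as a positive primary result, and under 2.7.A and 8 as a null one. Nothing in the text prevents the choice from being made after the data are seen. The plan sets itself a 5% overall error rate, so it has to say which tests that rate covers. The pilot is meant to inform a larger trial, so the choice of headline scale could carry into that trial's design.

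**Working it through.** **1. Reproduce the plan's own figures.** Inputs from 2.7.A: SD 2.9, 13 completers per arm, two-sided alpha 0.05/2 = 0.025, 80% power, two-sample t-test (24 df).

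- Standard error of a difference: 2.9 × √(2/13) = 1.137.
- 95% interval width: 2 × t(0.975; 24) × 1.137 = 2 × 2.064 × 1.137 = 4.70. The plan says 4.7.
- Power at 3.8 (noncentral t, noncentrality 3.8/1.137 = 3.34): 82.2%. The exact 80%-power difference is 3.70, so the stated 3.8 is slightly conservative, and 13 per arm is the smallest number that reaches 80% at 3.8.

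These figures fit a family of two tests on severity alone.

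**2. Bound the error if there are two scales.** With Hochberg run separately on each scale at 5%, the family-wise error is at most 0.05 + 0.05 = 10%. It is 1 − 0.95² = 9.75% if the scales are independent and each family spends its full 5%.

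**3. Simulate it.** Three arms of 13, shared placebo arm, pooled variance (36 df), two-sided tests, no effect of either drug on either scale (the global null), 400,000 trials per correlation. The severity-interference correlation is an assumption.

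| Rule | 0 | 0.5 | 0.7 | 0.9 |
|---|---|---|---|---|
| Hochberg within each scale, either may count | 9.3% | 8.7% | 8.1% | 6.9% |
| of which interference alone is positive | 4.5% | 4.0% | 3.4% | 2.1% |
| One Hochberg family over four p-values | 4.6% | 4.5% | 4.2% | 3.6% |
| Both scales required, Hochberg on each drug's larger p-value | 0.1% | 0.7% | 1.3% | 2.7% |

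Severity alone, with Hochberg over the two comparisons, gives 4.7 to 4.8% throughout. Independent repeat runs agree to about 0.1 percentage point.

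**4. Price a four-test family.** At alpha 0.05/4 = 0.0125, 13 per arm and SD 2.9, the detectable difference for severity rises from 3.70 to 4.07, and power at 3.8 falls from 82.2% to 73.4%. Reaching 80% at 3.8 needs 15 completers per arm, which is 3 × 15 = 45, everyone randomised with no dropout. These are Bonferroni figures, as in 2.7.A. With Hochberg itself, power for a 3.8-point severity effect goes from 84% (two tests) to 76-78% (four tests) when one drug works. When both drugs work on both scales it goes from 89% to 86-87%. The interference SD is assumed to be 2.9 here.

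**5. Check the rule that both scales must succeed.** The global null is not the worst case for this rule. Let one drug affect severity only and the other interference only, so that neither should pass. Hochberg run within each scale then errs 7.3 / 6.5 / 5.8 / 5.0% at a 3.8-point effect (correlations 0 / 0.5 / 0.7 / 0.9). It reaches 9 to 10% only at effects of about 6 points or more on the 0-10 scale. Hochberg on the larger of each drug's two p-values stays at or below about 5%.

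**The case against.** The best defence is that this is a pilot. Section 2.7.A makes estimation the main aim and calls the power calculation illustrative; section 6.6 plans no interim efficacy analysis. Mean differences and 95% intervals do not depend on which scale is called primary. All of that stands, and it limits the weight of the point.

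A second defence is that the text really means one variable. The wording in 2.2 and 8.1 is singular, with one 0-10 score, and a combined score would need only two tests, which Hochberg as written would cover. But no combined score is defined anywhere, and the heading over the definition in 2.2 is plural. This reading is open but not established.

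A third is that severity and interference are plainly co-primary, because 2.2, 8.1 and the outcome list in 3.1 all pair them. That is fair evidence of intent. It does not explain why section 8, immediately before 8.1, names severity alone, and it would leave four tests under a two-test adjustment.

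Three stronger inferences are tempting, and the documents support none of them:

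- **That the trial has a 9% error rate.** That needs a rule that either scale may count, which no section states, and a low correlation, which is assumed.
- **That an either-scale rule is the only way to exceed 5%.** That is true under the global null. Step 5 shows that requiring both scales can also exceed 5% if Hochberg is run within each scale, though by little at 3.8 points.
- **That the plan already allowed for four tests,** because a normal approximation at alpha 0.0125 also gives a detectable difference of 3.80. Section 2.7.A states a t-test at 0.025, so the match is a coincidence.

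**Conclusion.** The contradiction is in the current text and should be fixed. Two sections define the primary outcome with two scales and two define it with one. Interference has no status if severity alone is primary, and the multiplicity rule covers two tests only.

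The size depends on the reading. With severity alone the stated 5% holds (about 4.8%). If 8.1 is applied to each scale and either may count, the error under the global null is about 7 to 9%. This rests on 13 completers per arm, normal data, and assumed correlations of 0 to 0.9 between the scales.

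The consequence is a risk that the headline result is selected after the fact. It is not a flaw in the estimates or intervals, and it does not undermine the pilot's main purpose.

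**What to change.** Before unblinding, make 2.2, 2.7.A, 8 and 8.1 name the same primary outcome and state the success rule. Which scale is primary is the sponsor's choice.

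- **Option A: severity is the single primary outcome.** Put interference first on the secondary list in 2.2. This fits the existing power text, and 8.1 already extends the primary method to secondary outcomes, so the skewness rule follows. Cost: interference loses primary status.
- **Option B: both scales stay primary and either may count.** Use one Hochberg family over all four p-values. Restate 2.7.A for severity at alpha 0.0125 (detectable difference about 4.1; power at 3.8 about 73%). Extend the skewness rule to interference, and give an SD for interference or say that none was available. Cost: the power loss in step 4.
- **Option C: a drug must succeed on both scales.** Run Hochberg on the larger of each drug's two p-values, not within each scale. Cost: power of about 70-79% for one drug that moves both scales by 3.8 points (SD 2.9 assumed for interference), and about 2% for a drug that moves severity only.
- **If a single combined score was meant,** define it and base 2.7.A on it. The two-test Hochberg step then suffices.

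Each option is a change of wording in four sections. None changes data collection or sample size.

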2.3 STUDY DESIGN

This is a randomized, double-blinded, 3-arm study of 45 participants with HIV, chronic pain (defined as any bodily pain of moderate to severe intensity lasting for ≥3 months), and past-year heavy alcohol use, defined by NIAAA criteria. The 45 participants will be randomly assigned to either naltrexone, gabapentin, or placebo, using permuted blocks, to ensure equal numbers in each arm. Patients and research staff will be blinded to randomization. Participants will be treated for 8 weeks, and then assessed for an additional 4 weeks post-treatment.

The study design and schedule for study visits and assessments is depicted in Figure 1. After consent and enrollment, participants will be randomly assigned to receive either low-dose naltrexone, gabapentin, or placebo. Participants will be randomized using permuted blocks, to ensure similar numbers within each arm. Patients and research staff will be blinded to randomization. Participants will be given 2 weeks of medication at baseline, 2-weeks, 4-weeks, and 6-week visits, with instructions to bring pill packs/leftover medications to the following visit. The schedule of study visits is as follows: baseline (pre-treatment), week 4 (on treatment), week 8 (on treatment), week 12 (post-treatment). At the 8 week visit, all assessments will occur (see Section 5). At week 4, we will assess for medication tolerability, discontinuation, treatment side effects, self-reported adherence to intervention medications, and pain (BPI) only. At week 12 (post-treatment), there will be an assessment of pain (BPI) and cold-pressor test to assess whether pain reverts back to pre-treatment levels. Weeks 1, 2, 6, and 7 will be short visits at which time a brief assessment of tolerability, side effects, and adherence will occur, and we will ensure that participants have their medications (e.g. have not been lost or stolen).

Figure 1: Study Design (UH3 Phase)

Page 5 of 44

2.4 STUDY SITE

Recruitment, enrollment, and all study visits will take place at the Laboratory of Clinical Pharmacology of Addictions at the First St. Petersburg Pavlov State Medical University (PSMU) in St. Petersburg, Russia. PSMU is the major educational, scientific, and clinical medical institution for northwestern Russia. If unable to recruit an adequate sample size at these sites, we will broaden our recruitment methods to include other clinical sites of care for HIV-positive persons throughout St. Petersburg. Recruitment beyond Pavlov State Medical University (PSMU) will occur at Russia ARCH network hospitals including the major clinical HIV hospitals (Botkin Infectious Disease Hospital, Leningrad Regional AIDS Center, St. Petersburg City AIDS Center) and addiction hospitals (Leningrad Regional Center for Addictions, St. Petersburg City Addiction Hospital). Blood specimens will be processed and analyzed at ImmunoBioService (IBS) under the direction of [name].

2.5 INCLUSION CRITERIA

To be eligible to participate in the trial, participants will need to meet the following inclusion criteria:

- 1. 18 years or older
- 2. HIV-positive
- 3. Chronic pain (present ≥3 months) of moderate to severe intensity
- 4. Heavy drinking past year (Based on NIAAA criteria: > 14 standard drinks per week/ > 4 drinks in a day for men; > 7 drinks in the past week/ > 3 drinks in a day for women.)
- 5. If female, negative pregnancy test and willing to use adequate birth control
- 6. Provision of contact information for 2 contacts to assist with follow-up
- 7. Address within 100 kilometers of St. Petersburg
- 8. Possession of a telephone (home or cell)
- 9. Able and willing to comply with all study protocols and procedures

2.6 EXCLUSION CRITERIA AT STUDY ENTRY

- 1. Not fluent in Russian
- 2. Cognitive impairment resulting in inability to provide informed consent based on research assessor (RA) assessment
- 3. Known active TB or current febrile illness
- 4. Breastfeeding
- 5. Known uncontrolled psychiatric illness (such as active psychosis)
- 6. Current suicidal ideation
- 7. History of hypersensitivity to naltrexone, gabapentin, or naloxone
- 8. Current use (past week) of illicit or prescribed opiates as documented by either self-report or positive urine drug test
- 9. Unwilling to abstain from opiates during the treatment period
- 10. Current use of neuroleptics
- 11. History of seizure disorder
- 12. Known liver failure
- 13. ALT/AST levels >5x normal
- 14. CrCl < 60 mL/min
- 15. History of Raynaud's disease
- 16. Planned surgeries in the next 3 months
- 17. Enrolled in another HIV and/or substance use medication intervention study
- 18. Taking naltrexone in the past 30 days
- 19. Taking gabapentin in the past 30 days
- 20. Taking pregabalin in the past 30 days
- 21. Diagnosis of chronic obstructive pulmonary disease (COPD)

2.7 RECRUITMENT GOALS

We aim to randomize 45 participants into the trial and a total of up to 60 may be enrolled, but not randomized due to not meeting study entry criteria. Existing Russia ARCH (H-31200) participants will be

offered to be screened for PETER PAIN. We will also screen St PETER (H-35288) participants at their final St PETER study visit for eligibility. Participants who have completed the LINC-II study (H-36706) will also be a potential recruitment source. Recruitment beyond PSMU will occur at local NGOs and Russia ARCH network hospitals including the major clinical HIV hospitals (Botkin Infectious Disease Hospital, Leningrad Regional AIDS Center, St. Petersburg City AIDS Center) and addiction hospitals (Leningrad Regional Center for Addictions, St. Petersburg City Addiction Hospital).

2.7.A. SAMPLE SIZE CALCULATION AND POWER

The purpose of the pilot trial is to generate preliminary data for design of a future larger RCT to demonstrate efficacy. Thus estimation rather than testing is the main objective of this aim. However we provide illustrative power calculations for our primary outcome (change in pain severity) based on prior literature and the number of participants (15 in each arm) we intend to study. It is expected that 45 participants will be enrolled into the study and less than 15% will drop out by 8 weeks. We therefore assume 39 participants (13 per arm) will complete the 8-week follow-up. The following calculations assume 2-sided tests, with an overall significance level of 0.05. For the purposes of power calculations, we consider a simple, conservative setting based on a Bonferroni adjustment for multiple comparisons, although in our analyses we will use the Hochberg sequential correction method, an approach that will result in higher power than the Bonferroni method. To maintain an overall type I error rate of 5%, we assume each of the 2 primary pairwise comparisons (i.e. each intervention vs. placebo) will be conducted at an alpha level of 0.025 for the following power calculations. Based on the 2013 study by Younger, the standard deviation for change in pain severity was 2.9. We expect the standard deviation will be similar in the proposed study and the same for each randomized group. Given this assumption, the minimum detectable difference in change in pain severity between baseline and 8 weeks that the study can detect with 80% power is 3.8 for either of the 2 primary comparisons of interest (i.e., naltrexone vs. placebo; gabapentin vs. placebo), (e.g., -3.0 vs. 0.8 for naltrexone vs. placebo, respectively) using a 2-sided t-test. Because a main goal of the study is estimation of effect sizes for the design of a future study, we also estimate the width of the confidence interval for the mean difference between any two arms for the primary outcome. Our calculations assume 2-sided 95% confidence intervals. Assuming a standard deviation of 2.9 as above, the 95% confidence interval for the mean difference in change in pain severity for either intervention arm vs. placebo would be no wider than 4.7.

